2.4.4 Other safety data

2.4.4.1 ECG

A listing of all newly occurring or worsening abnormalities (based on the treatment period/study period) will be provided, as well as a by-subject listing of all quantitative ECG parameters. Notable abnormal QTc will be defined as:

QTc > 500 msec

QTc > 480 msec

QTc > 450 msec

QTc changes from baseline > 30 msec

QTc changes from baseline > 60 msec

PR > 250 msec

2.4.4.2 Vital signs

Analysis in vital sign measurement using descriptive summary statistics for the change from baseline for each post-baseline visit will be performed by vital sign and treatment group. Change from baseline will only be summarized for subjects with both baseline and post-baseline values and will be calculated as:

change from baseline = post-baseline value – extension baseline value

The number and percentage of subjects with newly occurring notable vital signs will be presented. Criteria for notable vital sign abnormalities are provided in Table 2-5 below. A listing of subjects with newly occurring notably abnormal vital signs will be provided.

Table 2-5	Criteria for notable vital sign abnormalities
-----------	---

Vital sign (unit)	Notable abnormalities
Systolic blood pressure (mmHg)	Either an increase of \ge 30 that results in \ge 180 or $>$ 200 (mm/Hg) OR a decrease of \ge 30 that results in \le 90 or $<$ 75 (mm/Hg)
Diastolic blood pressure (mmHg)	Either an increase of ≥ 20 that results in ≥ 105 or > 115(mm/Hg) OR a decrease of ≥20 that results in ≤ 50 or < 40 (mm/Hg)
Pulse (bpm)	> 100 bpm or <40 bpm

2.5 Pharmacokinetic and immunogenicity endpoints

PK data will be analyzed in PK set by iscalimab treatment. To preserve blinding of treatment assignment, the PK data will be accessible to blinded personnel in the CTT only after unblinding for the primary analysis.

Trough free plasma concentration (C-trough in microg/mL) of iscalimab will be directly derived from the bioanalytical data and loaded into clinical database.

Time (days) elapsed since the first dose (Elapsed Time #1 with reference to the Dose Reference ID #1 – as defined in the Blood Log) of iscalimab will be derived (date of PK blood sampling – date of first dose of iscalimab treatment) + 1) and compared to the analysis windows defined in Table 2-1 to assign the values to analysis visits. If multiple measurements fall within the same analysis window, the algorithms outlined in Table 2-1 will be used to choose the value for the visit.

Also, with reference to the Dose Reference ID #2 (as defined in the Blood Log), Elapsed Time #2, the time (days) elapsed since the specified dose, will be derived and reported as well in the merged file.

Descriptive summaries of C-trough will be presented by iscalimab treatment and analysis visit. Summary statistics will include mean (arithmetic and geometric), SD, coefficient of variation (CV) (arithmetic and geometric), median, minimum and maximum. Concentrations below LLOQ will be treated as zero in summary statistics and the frequency (n, %) of concentrations below the LLOQ will be provided.

Trough plasma iscalimab concentrations overtime (elapsed time since first dose) for patients will be presented with spaghetti plots for each iscalimab treatment group. All concentration measurements will be plotted based on the actual day/time of assessment after the first dose date of iscalimab treatment.

A listing by cohorts, iscalimab treatment, patient number and CRF visit will also be produced.

The Ctrough,ss (steady state Ctrough) will be directly extracted from the bioanalytical data and summarized by iscalimab treatment groups for mean (arithmetic and geometric), SD, coefficient of variation (CV) (arithmetic and geometric), median, minimum and maximum.

Immunogenicity results will be listed by treatment arm, subject, and visit for subject who received at least one dose of iscalimab. Incidence of anti-drug antibody positive subjects (ADA+) may be calculated by iscalimab dose level and analysis visit defined based on time since first dose of iscalimab. Subjects' data from both cohorts will be pooled according to the iscalimab dose levels.

•

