As demonstrated in the PoC Study CCFZ533X2203 in pSS, a single s.c. dose of 600 mg iscalimab at Day 1 will deliver plasma concentrations generally above 40 µg/mL after 1 week. Subsequent weekly doses on Week 61 and 62 in Arms 1 and 2 are expected (i) to maintain CFZ533 plasma levels above 40 µg/mL, and (ii) to deliver iscalimab trough levels that are close to expected steady state conditions.

Further supportive arguments on the selected loading dosing regimen are provided in the Rationale for dose/regimen and duration of treatment of the TWINSS core study protocol (refer to Section 4 of the core study protocol).

Rationale for maintenance regimen

The maintenance regimen of 600 mg s.c. Q2W is expected to provide a median steady state trough plasma level at about 144 µg/mL (90% of the population within 282 - 46 µg/mL), in the upper range of trough levels observed in the PoC Study CCFZ533X2203-Cohort 2 (i.v. regimen; these concentrations were associated with clinical efficacy and suppression of a biologically relevant biomarker CXCL13 - a marker of germinal center activity).

The maintenance regimen of 300 mg s.c. Q2W is expected to deliver a median steady state trough plasma level at about 54 µg/mL (90% of the population within 125 - 0.1 µg/mL), with a reasonable chance to show efficacy in SjS.

The between subject variability in exposure within the two treatment arms (to a lesser extent in the 600 mg treatment arm) is likely to depend on the biology of CD40 in target tissues (expression level, turnover) and its potential modulation during the treatment period.

Rationale for the duration of the safety follow-up period (target engagement after the last dose)

Based on predicted median CFZ533 plasma concentration-time profile at 600 mg s.c. Q2W regimen, at about 14 weeks after the last dose, iscalimab plasma concentrations are expected to drop below 20 µg/mL with no expected pharmacodynamic activity in target tissues (e.g., germinal centers; data from non-human primates - please see current IB).

A 12-week follow-up period (14 weeks after the last dose) has been selected for the study and is justified to monitor for any related serious adverse events (SAE).

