^X Assessment to be recorded in the clinical database or received electronically from a vendor

¹ Corresponds to the Week 60 visit of the core study. Assessments carried out as part of Week 60 as per core study protocol should be used for Week 60E1 of the extension study.

² Optional site visits - Week 66, 70, 74, 78, 82, 86, 90, 94, 98, 102, 106. Participants who are unable to self-administer the PFS injections at home will visit the site and site staff will supervise self-administration or administer the PFS injection for them. Other participants who can self-administer the PFS injection can do so at home at these optional visits.

³ Informed consent should be obtained before commencement of the Week 60 assessments of the core study.

⁴ Contact IRT for new treatment reassignment.

⁵ AEs/SAEs occurring after the participant has signed the informed consent must be captured on the appropriate eCRF page.

⁶ C - These assessments shall be conducted as part of the core study CCFZ533B2201 and will not be repeated in this extension study

⁷ S - Assessment to be recorded in the source documentation only

⁸ [REDACTED]

⁹ Local lab testing of CMV IgG, IgM and DNA (by PCR) must be performed every 3 months until end of study. Hepatitis B monitoring applicable to HBsAg (-) patients who were HBcAb (+) and HBV DNA (-) at screening during the core study. Local lab testing of HBsAg and HBV DNA must be performed every 3 months until end of study.

¹⁰ While on treatment, coagulation monitoring applies only to participants who have antiphospholipid antibodies (lupus anticoagulant, anti-cardiolipin antibodies) and/or who are on pre-existing antithrombotic therapy/prophylaxis, as reflected in the exclusion criteria of the TWINSS core study protocol.

¹¹ Analysis of cryoglobulins will be done only for participants who were positive at screening in the TWINSS core study.

¹² Urine pregnancy tests will be performed throughout the study

¹³ Blood sample is collected pre-dose.

¹⁴ [REDACTED]

¹⁵ [REDACTED]

¹⁶ Optional [REDACTED]

¹⁷ [REDACTED]

¹⁸ [REDACTED]

¹⁹ In case of premature discontinuation, participants will enter the follow-up after completing assessments for this visit.

²⁰ Mandatory to all participants, including those who have discontinued the study prematurely.

²¹ Week 106 is the last dose administration visit in the Treatment Period.

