8.4.3 Pregnancy and assessments of fertility

All pre-menopausal women who are not surgically sterile will have local urine pregnancy tests monthly, as indicated in [Table 8-1](#). Additional pregnancy testing might be performed if requested by local requirements. A positive urine test requires immediate interruption of study drug and needs to be confirmed with a serum β -hCG test (serum pregnancy test). If positive, the participant must be discontinued from the study treatment. Highly effective method of birth control must be used for women of childbearing potential (see exclusion criteria definitions, [Section 5.2](#)). In consideration of the patient population and overall iscalimab risk benefit profile, women of child-bearing potential must utilize highly effective contraception methods to avoid becoming pregnant while receiving iscalimab and for 14 weeks after the last dose or until data from the reproductive toxicity studies suggest otherwise. Women who are nursing may not participate in this trial. The washout period of 14 weeks after the last dose is justified based on predicted PK profiles at 10 mg/kg, where iscalimab is predicted to be fully cleared from plasma and tissues, with no residual pharmacodynamic activity.

If participants cannot visit the site to have pregnancy tests, urine pregnancy test kits may be used. Relevant participants can perform the urine pregnancy test at home and report the result to the site. It is important that participants are instructed to perform the urine pregnancy test first, and only if the test result is negative are they to proceed with administration of the study treatment. A communication process should be established with the participant so that the site is informed and can verify the pregnancy test results (e.g., following country-specific measures).

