12.5 Analysis of secondary endpoints/estimands

12.5.1 Pharmacokinetics

Trough free iscalimab plasma concentrations will be listed by treatment arm, subject, and visit/sampling time point.

Descriptive summary statistics will be provided by iscalimab dose level and analysis visits, including the frequency (n, %) of concentrations below the LLOQ. Summary statistics will include mean (arithmetic and geometric), SD, coefficient of variation (CV) (arithmetic and geometric), median, minimum and maximum.

Concentrations below LLOQ will be treated as zero in summary statistics.

The following PK parameters will be determined: trough concentration (C_{trough}), steady state (ss), and will be directly derived from the bioanalytical data (summary statistic tables; no non-compartmental analysis will be performed).

For each iscalimab concentration (or sample), an elapsed time since first (and last) dose of iscalimab will be calculated based on a Dose Reference ID (provided in the Blood Log). The time window for deriving the elapsed time will be defined in the SAP.

Graphical presentation of the data will be provided.

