1.2 Study objectives and endpoints

The objectives and related endpoints planned in the Clinical Study Report (CSR) are listed in Table 1-1.

Table 1-1 Objectives and related endpoints

Objective(s)	E	Endpoint(s)				
Primary objective(s)	E	Endpoint(s) for primary objective(s)				
• To evaluate the safety and iscalimab at two dose level 300 mg) in patients with Sj participated in the TWINSS CCFZ533B2201	tolerability of s (600 mg and S, who S core study,	Incidence of Treatment-emergent adverse events (TEAEs)/ serious adverse events (SAEs) Routine hematology and clinical chemistry laboratory test results at analysis visits up to end of study Vital signs at analysis visits up to end of study				
Secondary objective(s)	E	ndpoint(s) for secondary objective(s)				
 To assess the pharmacokin levels) and dose-exposure iscalimab 	netics (PK trough • relationship of	Free iscalimab concentration in plasma during the treatment (Ctrough) and follow- up (up to end of study) periods				
• To assess immunogenicity	of iscalimab •	Incidence of anti-iscalimab antibodies in plasma at analysis visits up to end of study				

2 Statistical methods

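### Setting values below the LLOQ to zero leaves the geometric mean and CV of iscalimab zero or undefined in any cell with such a value, and tying ADA analysis to the PK Set can drop participants whose PK samples are all below the LLOQ

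*SAP*

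**What the plan says.** **Rule for BLQ values.** SAP 2.5 states "Concentrations below LLOQ will be treated as zero in summary statistics". Protocol 12.5.1 has the same rule, and Protocol 8.5.2 has the laboratory report such values as zero and label missing results separately.

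**Statistics required.** SAP 2.5 states "Summary statistics will include mean (arithmetic and geometric), SD, coefficient of variation (CV) (arithmetic and geometric), median, minimum and maximum". Protocol 12.5.1 asks for the same set and adds "Descriptive summary statistics will be provided by iscalimab dose level and analysis visits, including the frequency (n, %) of concentrations below the LLOQ". SAP 2.5 repeats the geometric statistics for Ctrough,ss, which "will be directly extracted from the bioanalytical data and summarized by iscalimab treatment groups". Neither document gives a separate BLQ rule for the geometric statistics.

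**Where BLQ values may arise.** Protocol 4.2 predicts a median 300 mg trough of about 54 µg/mL, with "90% of the population within 125 - 0.1" µg/mL. The secondary PK endpoint covers the treatment "and follow- up (up to end of study) periods" (SAP Table 1-1). PK samples are taken at Weeks 76, 92, 108 and 120 (Protocol Table 16-5). A footnote to Protocol Table 8-1 says "Week 106 is the last dose administration visit in the Treatment Period".

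**Analysis sets.** The SAP section on analysis sets admits to the PK Set (PKS) dosed participants who have quantifiable drug measurements. It defines an IM Set in parallel terms. The IM Set paragraph then says that immunogenicity is analysed on PKS, and ends by describing summaries in the IM Set. SAP 2.5 lists ADA results for everyone dosed and makes the ADA incidence summary optional, although ADA incidence is a listed secondary endpoint.

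**The concern.** The geometric mean and geometric CV work on logarithms, and zero has none. The plan therefore prescribes statistics that its own BLQ rule makes impossible wherever a BLQ value occurs. If the team then chooses a workaround after seeing the data, that choice determines the reported 300 mg geometric mean.

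The set definitions raise a related problem. Participants with no quantifiable drug at any visit have the lowest exposure, yet the PK Set wording removes them from the Ctrough summary and from the count of BLQ values. If ADA incidence also uses PKS, they leave that denominator too. Protocol Table 4-1 (Risk 4) says that an immune response could be correlated with loss of exposure, so some of those removed could be ADA-positive.

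**Working it through.** The plan gives no figure to reproduce. The inputs from the documents are the predicted 300 mg range (0.1 / 54 / 125 µg/mL), the predicted 600 mg range (46 / 144 / 282 µg/mL), the sampling days and the 206 enrolled. The LLOQ, BLQ rate and arm split are assumptions.

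**1. Effect of one zero.** Geometric mean = exp(mean of ln x). Geometric CV = sqrt(exp(variance of ln x) − 1). In 100 simulated troughs (lognormal, median 54, assumed log-SD 0.5):

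| Zeros among 100 | Geometric mean | Geometric CV |
|---|---|---|
| 0 | 52.0 | 45% |
| 1 | 0 | undefined |
| 5 | 0 | undefined |

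**2. Where it can occur.**
- 300 mg on treatment: if the range is a central 90% interval, 5% of troughs lie below 0.1 µg/mL. An LLOQ near that level implies about 5% BLQ.
- 600 mg on treatment: the lower limit is 46 µg/mL, so BLQ values are not expected.
- Week 120: Day 841 − Day 743 (Week 106, last dose) = 98 days = 14 weeks. Protocol 8.4.3 describes 14 weeks, at 10 mg/kg, as a point "where iscalimab is predicted to be fully cleared from plasma and tissues, with no residual pharmacodynamic activity". Protocol 4.2 says only that the 600 mg median falls below 20 µg/mL. BLQ values are possible there, at an unknown rate.

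**3. Chance that a 300 mg cell is affected.** P(at least one BLQ) = 1 − (1 − p)^n, for an assumed 40 to 150 participants on 300 mg:
- p = 5%: 1 − 0.95^40 = 87%; 1 − 0.95^150 = 99.95%.
- p = 0.5%: 1 − 0.995^40 = 18%; 1 − 0.995^150 = 53%.

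**4. How much the workaround matters.** Let G be the geometric mean of the quantifiable values and p the BLQ share. Substituting LLOQ/2 gives G^(1−p) × (LLOQ/2)^p, so dropping zeros is larger by the factor (G ÷ (LLOQ/2))^p. Take p = 0.05 and LLOQ 0.1, with two assumed curves through the stated 300 mg percentiles:

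| Curve | Zeros dropped | LLOQ/2 | Factor |
|---|---|---|---|
| Piecewise-linear distribution, 0 to 200 µg/mL | 44.9 | 32.0 | (44.9/0.05)^0.05 = 1.40 |
| Split lognormal, lower log-SD 3.825, upper 0.510 | 20.3 | 15.1 | (20.3/0.05)^0.05 = 1.35 |

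The factor isolates the effect of the rule; the gap between the two rows reflects only the assumed curve. The median is 54 under both curves with BLQ set to zero.

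**5. Loss from the PK Set.** With 5% BLQ per sample and three on-treatment samples, the share with all three BLQ runs from 0.05^3 = 0.0125% (independent samples) to 5% (the same people each time). A quantifiable Week 120 value would keep a participant in the set, so the true loss can only be smaller.

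**6. ADA incidence.** Assume 103 in an arm, 8 ADA-positive and 5 with all samples BLQ. All dosed: 8/103 = 7.8%. On PKS: 3/98 = 3.1% if all five are ADA-positive, or 8/98 = 8.2% if none is.

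**The case against.** The study is descriptive, and no decision in the documents rests on the geometric mean. The arithmetic mean, median, minimum, maximum, BLQ count, listings and spaghetti plots all remain, and a zero or blank cell is visible to any reader. The reference to PKS in the IM Set paragraph looks like a copying slip, since the paragraph ends with the IM Set, and the ADA listing covers everyone dosed. Protocol Table 4-1 also expects the drug to suppress responses against itself. All of this stands and limits the importance of the point. It does not supply a usable geometric rule or settle the ADA denominator.

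Three stronger readings are tempting but unsupported:
- *All planned geometric statistics fail.* Only cells containing a BLQ value do, and the 600 mg on-treatment cells are not expected to be among them.
- *Week 120 will be largely BLQ.* The clearance statement is a contraception rationale at 10 mg/kg. The study-specific prediction is only a 600 mg median below 20 µg/mL, and no BLQ rate is given.
- *The sets hide many participants or bias ADA incidence downwards.* Loss requires every PK sample to be BLQ. An early stopper is weak evidence for it, because dosing starts with 600 mg, which Protocol 4.2 says generally gives over 40 µg/mL after one week. The direction of any ADA shift depends on who is lost.

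**Conclusion.** The point holds, limited to cells with at least one BLQ value. There the plan's two instructions cannot both be met: the geometric mean is 0 or not computable, and the geometric CV is undefined. That part needs no assumption.

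The size is illustrative: a factor of roughly 1.35 to 1.4 in the 300 mg geometric mean between two common workarounds. It rests on about 5% BLQ, an LLOQ near 0.1 µg/mL and assumed curve shapes.

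The set definitions are a separate, real conflict. They leave the ADA denominator unsettled and can remove participants with only BLQ samples from both secondary summaries, though probably few. The SAP should be corrected on both counts. Neither affects the primary safety objective.

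**What to change.** - **SAP 2.5:** keep BLQ = 0 for the arithmetic mean, median, minimum and maximum. Compute the geometric mean and CV with BLQ set to LLOQ/2, and show the quantifiable-only value with its n alongside, for each visit and for Ctrough,ss. Declaring the cell not computed would leave the same blank as now.
- **PK Set:** dosed participants with at least one valid concentration result, BLQ included.
- **IM Set:** dosed participants with at least one valid ADA result, positive or negative. Analyse ADA incidence on this set, not on PKS.
- **SAP section 3:** record these changes; it now lists only the TEAE definition.

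No new samples or visits are needed. The zeros already identify BLQ records, so the programmer needs only the LLOQ value. The cost is slightly more programming, and reported 300 mg exposure may be lower.

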There is a hypothetical risk for thromboembolic complications when targeting this co-stimulatory pathway. This risk is based on clinical results from previous compounds (e.g. BG9588, IDEC-131) which have targeted CD154 (CD40 ligand) and resulted in a fatal hyper-coagulation phenotype.

Although the risk is theoretical, hematologic and coagulation parameters will be monitored in the current study. Furthermore, participants with conditions such as antiphospholipid syndrome, who are at a higher risk for thromboembolism, will be excluded unless they are receiving antithrombotic prophylaxis. CFZ533 binds to CD40 receptor and is Fc-silent mAb hence does not appear to carry the same risk of thrombosis. Both preclinical and clinical data from an extensive Phase 2 clinical program across healthy subjects and participants across different indications have not indicated a risk of thrombosis with CFZ533.

Risk 4 Immunogenicity

As with any monoclonal antibody, there is a hypothetical risk of developing anti-CFZ533 antibodies. However, it is likely that CFZ533 doses will achieve complete receptor occupancy during the treatment period. In these conditions, it is expected that CFZ533 will retain its capacity to block immune responses, including those directed against the drug itself, neutralizing or not.

Samples will be collected during study to assess immunogenicity. Immunogenicity will be monitored during clinical development and the consequences of an immune response to CFZ533 could be correlated with, a loss of exposure (PK), a loss of peripheral CD40 receptor occupancy (PD), and/or the appearance of immune related adverse events including injection site reactions.

Risk 5 Vaccination Failure

Vaccination of participants during treatment with CFZ533 and prior to clearance of the antibody is likely to result in therapeutic failure (i.e., non-protective antibody titers) due to the pharmacologic activity of the antibody. Administration of live attenuated vaccines should be avoided while receiving CFZ533 treatment and for at least 14 weeks thereafter.

One fatal event (potential CMV infection) was reported in the CCFZ533X2202 clinical trial in Lupus nephritis, suspected to be related to the study medication by the Investigator.

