¹ [REDACTED] ² While on treatment, coagulation monitoring applies only to participants who have antiphospholipid antibodies (lupus anticoagulant, anti-cardiolipin antibodies) and/or who are on pre-existing antithrombotic therapy/prophylaxis, as reflected in the exclusion criteria of the TWINSS core study protocol. ³ Analysis of cryoglobulins will be done only for participants who were positive at screening in the TWINSS core study. ⁴ Blood sample is collected pre-dose. ⁵ Corresponds to the Week 60 visit of the core study. Assessments carried out as part of Week 60 as per core study protocol can be used for Week 60E1 of the extension study. ⁶ In case of premature discontinuation, participants will enter the follow up after completing assessments for this visit. ⁷ Mandatory to all subjects, including those who have discontinued the study prematurely.													

[figure not shown]
Table 16-6 (B) - Blood Logs

[figure not shown]
Period	Visit Name	Days	Weeks	Immunogenicity ¹		Total (mL)
				Size (mL)	Sample ID	
Extension-Treatment	Wk 60E1 ²	421	60	-	-	0
	Wk 61	428	61	-	-	0
	Wk 62	435	62	-	-	0
	Wk 64	449	64	-	-	0
	Wk 66	463	66	-	-	0
	Wk 68	477	68	-	-	0
	Wk 70	491	70	-	-	0
	Wk 72	505	72	-	-	0
	Wk 74	519	74	-	-	0
	Wk 76	533	76	4	201	6
	Wk 78	547	78	-	-	0
	Wk 80	561	80	-	-	0
	Wk 82	575	82	-	-	0
	Wk 84	589	84	-	-	0
	Wk 86	603	86	-	-	0
	Wk 88	617	88	-	-	0
	Wk 90	631	90	-	-	0
	Wk 92	645	92	4	202	6
	Wk 94	659	94	-	-	0
	Wk 96	673	96	-	-	0
Wk 98	687	98	-	-	0	
Wk 100	701	100	-	-	0	
Wk 102	715	102	-	-	0	

[figure not shown]
Period	Visit Name	Days	Weeks	Immunogenicity ¹		Total (mL)
				Size (mL)	Sample ID	
	Wk 104	729	104	-	-	0
	Wk 106	743	106	-	-	0
	Wk 108/TD ³	757	108	4	203	6
Post-Treatment Follow-Up	Wk 112	785	112	-	-	0
	Wk 120/EOS ⁴	841	120	4	204	6
Total 24.0 mL						

[figure not shown]
¹ Blood sample is collected pre-dose. ² Corresponds to the Week 60 visit of the core study. Assessments carried out as part of Week 60 as per core study protocol can be used for Week 60E1 of the extension study. ³ In case of premature discontinuation, participants will enter the follow up after completing assessments for this visit.

[figure not shown]
⁴ Mandatory to all subjects, including those who have discontinued the study prematurely.

[figure not shown]

[figure not shown]

[figure not shown]

[figure not shown]

[figure not shown]

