Full Analysis Set (FAS): The FAS comprises all participants to whom study treatment for the extension study has been assigned by the re-assignment algorithm. For analysis on FAS, participants will be analyzed according to the treatment group to which they have been assigned. Only data in the extension study will be included in the analysis.

Summaries of extension data in FAS will be based on the core study cohort assignment and reassigned treatment groups.

- Cohort 1 CFZ533 600 mg
- Cohort 1- CFZ533 300 mg
- Cohort 2 CFZ533 600 mg
- Cohort 2 CFZ533 300 mg

Safety Set (SAF): The Safety Set includes all subjects who received at least one dose of study treatment. Subjects will be analyzed according to the actual treatment received. The safety set will be used in the analysis of all safety variables.

The actual treatment received in a period is defined as the treatment dose level (including loading dose) that a subject was most frequently exposed to during the period. The frequency will be calculated using data collected on the Dose Administration Record (DAR). In case a subject is exposed to more than one dose level for the same number of times during a period, the actual treatment is the earliest one administered to the subject in that period.

Summaries of extension data in SAF will be based on the re-assigned treatment groups.

- CFZ533 600 mg
- CFZ533 300 mg

The PK Set (PKS) includes all subjects who received at least one dose of iscalimab treatment and have quantifiable PK measurements of iscalimab. Analysis of plasma PK, will be based on PKS and by the iscalimab treatment dose level a subject is most frequently exposed to, including the loading dose, during the study. Only data in the extension study will be included in the analysis.

Summaries of extension data in PKS will be based on the re-assigned treatment groups.

- CFZ533 600 mg
- CFZ533 300 mg

The IM Set (IMS) includes all subjects who received at least one dose of iscalimab treatment and have quantifiable immunogenicity measurements of iscalimab. Analysis of immunogenicity data will be based on PKS and by the iscalimab treatment dose level a subject is most frequently exposed to, including the loading dose, during the study. Only data in the extension study will be included in the analysis.

Summaries of extension data in IMS will be based on the re-assigned treatment groups.

- CFZ533 600 mg
- CFZ533 300 mg

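### The SAP counts antibody-positive participants by visit without using baseline antibody status, so antibodies already present at entry are reported as extension incidence

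*SAP*

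**What the plan says.** The secondary immunogenicity endpoint (Protocol Table 2-1, repeated in SAP 1.2) is "Incidence of anti-iscalimab antibodies in plasma at analysis visits up to end of study".

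SAP 2.5 lists all ADA results by arm, subject and visit. It adds that "Incidence of anti-drug antibody positive subjects (ADA+) may be calculated by iscalimab dose level and analysis visit defined based on time since first dose", with both core cohorts pooled by dose level. It defines no treatment-emergent, induced or boosted ADA.

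The IM Set paragraph in the SAP's analysis-set section states: "Only data in the extension study will be included in the analysis".

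The immunogenicity blood log (Protocol 16.5, Table 16-6) has no extension sample at entry; the row reads "Wk 60E1 ² 421 60 - - 0". Samples are listed at Weeks 76, 92, 108 and 120. A footnote to that log says: "Assessments carried out as part of Week 60 as per core study protocol can be used for Week 60E1 of the extension study". Footnote 1 to Protocol Table 8-1 is firmer and says that the core Week 60 assessments should be used.

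SAP 2.1.1.3 defines baseline as the last assessment before the first extension dose. Protocol 12.5.3 offers ADA summary statistics and shift tables only if appropriate, and SAP 2.5 does not mention shift tables.

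**The concern.** Nobody enters this study untreated. Protocol 16.11 moves the core placebo arms to iscalimab at Week 24 and keeps the other arms on it throughout, so entrants have had one or two 24-week periods of drug followed by the core follow-up.

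That drug-free interval is a plausible time for antibodies to appear. Under Risk 4 in Protocol 4.5, given complete receptor occupancy during treatment, "it is expected that CFZ533 will retain its capacity to block immune responses, including those directed against the drug itself, neutralizing or not". Protocol 4.2 expects no pharmacodynamic activity in target tissues about 14 weeks after the last dose of the 600 mg regimen. The protocol does not discuss ADA in the off-drug interval, so this is an inference from its reasoning.

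A by-visit count that ignores entry status mixes antibodies carried in with antibodies formed in the extension. The objective concerns the immunogenicity of iscalimab, the count is by dose level, and Protocol 1.2 says that the extension's safety data may inform Phase III design. A reader would take a figure labelled incidence for 600 mg or 300 mg as something that arose on that dose in this study.

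**Working it through.** **1. Timing, from the schedules.**
- Extension doses (Protocol 3 and 6.7.2): Weeks 60, 61, 62, then 64 to 106 every two weeks. That is 3 + 22 = 25, the number stated. The gap to end of study is 120 − 106 = 14 weeks, also as stated (Protocol 4.1).
- Core Period 2 (Protocol 16.11): 13 administrations. Doses at Weeks 24, 25, 26, then 28 to 46 every two weeks give 3 + 10 = 13. The last core dose is therefore at Week 46, and 60 − 46 = 14 weeks off drug before entry.
- First extension ADA sample: Week 76, Day 533. Relative to entry on Day 421 this is 533 − 421 + 1 = study day 113. Doses before this pre-dose sample: Weeks 60, 61, 62, 64, 66, 68, 70, 72, 74 = 9. Time since the last core dose: 76 − 46 = 30 weeks.

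**2. What the count contains.** Positives at a visit = carried in and still detectable (C) + new in the extension (N). SAP 2.5 reports C + N; incidence would be N among those negative at entry.

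**3. Size.** The documents give no ADA rate. SAP 1.1 gives 206 enrolled, and 206 × 1% ≈ 2 participants. Purely as an illustration, assuming all carried-in antibodies remain detectable:
- 2–10% carried in (4–21) and 1–3% new (2–6): the table shows 6–27 positives against 2–6 new cases.
- Rates reversed: the same 6–27 positives, of which 4–21 are new.

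The visit counts alone cannot separate these two cases.

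**4. Balance between arms.** Protocol 6.1.3: all core 600 mg participants stay on 600 mg; 150 mg and 300 mg responders go to or stay on 300 mg; 150 mg and 300 mg non-responders go to 600 mg. Let n be the number at a core dose, a its ADA rate, and r₊ and r₋ the response rates in ADA-positive and ADA-negative participants. With sums over core 150 and 300 mg:
- 300 mg arm: positives = Σ n·a·r₊; size = Σ n·[a·r₊ + (1 − a)·r₋].
- 600 mg arm: positives = n₆₀₀·a₆₀₀ + Σ n·a·(1 − r₊); size = 206 − size of the 300 mg arm.

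All rates and mixes here are assumptions. Worked for a core mix of 40/60/106 at 150/300/600 mg with r₋ = 50%:
- ADA 5% at every dose, r₊ = 25%. 300 mg: (2 + 3) × 0.25 = 1.25 of 48.75 = 2.6%. 600 mg: 5.3 + 3.75 = 9.05 of 157.25 = 5.8%.
- ADA 10/5/1%, r₊ = 50%. 300 mg: (4 + 3) × 0.5 = 3.5 of 50 = 7.0%. 600 mg: 1.06 + 3.5 = 4.56 of 156 = 2.9%.

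Across this mix and two others (32/32/142 and 69/69/68), r₋ = 50% throughout:

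| Assumed core ADA rate (150/300/600 mg) | r₊ | Carry-over, 300 mg arm | Carry-over, 600 mg arm |
|---|---|---|---|
| 5/5/5% | 50% | 5.0% | 5.0% |
| 5/5/5% | 25% | 2.6% | 5.4–6.2% |
| 10/5/1% | 50% | 7.0–7.5% | 2.2–4.3% |

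With rates of 10/5/1% or 10/5/2%, the 600 mg percentage is the higher one only if r₊ falls to about 19–37% or below, depending on the mix. The arms can differ, and the sign depends on facts that the documents do not give.

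**The case against.** The strongest reply is that a baseline already exists. SAP 2.1.1.3 defines one, Table 2-2 applies its baseline rule to all data, and the Week 60E1 footnotes bring in core Week 60 results. Nor does the extension-only wording plainly exclude them. Protocol 12.1 puts the same restriction on the Safety Set, and the blood log shows no hematology or chemistry draw at Week 60E1, yet SAP 2.4.3 plans change from extension baseline for both. Those baselines must come from the core visit. This stands, and a reader who inferred that the SAP has no baseline would be wrong. It does not answer the point, however. SAP 2.4.3 and 2.4.4.2 explicitly use the extension baseline for laboratory data and vital signs, and the latter counts newly occurring notable values; SAP 2.5 has no such rule for ADA.

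Second, the conditional shift tables in Protocol 12.5.3 are not withdrawn, since SAP section 3 lists only the changed adverse-event definition. True, but they remain optional, and a shift table beside an unadjusted count would not change what is called incidence.

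Third, the table is optional, by visit and descriptive, and the listing shows every result. This lowers the stakes. A descriptive label should still match what is counted.

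Fourth, parts of Table 8-1, the visit-window table and the text after SAP 2.5 are not visible, and the core sampling schedule is not in these documents. The point therefore rests on what SAP 2.5 says, not on absent rows.

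**Conclusion.** The point holds. Followed as written, SAP 2.5 reports visit prevalence as incidence for a stated secondary endpoint, in a population that was wholly exposed before entry. It should be corrected, but it is a matter of labelling and interpretation in a descriptive study and affects no hypothesis test.

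Two stronger readings are tempting and are not supported.
- *Carry-over would collect in the 600 mg arm and look like a dose effect.* This needs ADA to go with non-response. Protocol 4.5 says only that an immune response could be correlated with loss of exposure. If ADA is commoner at low core doses and unrelated to response, the percentage is higher at 300 mg. Antibodies first appearing after the Week 48 (or Week 40) scores cannot influence the assignment at all. What can be said is that carry-over may be unequal, direction unknown.
- *Most of the reported incidence would be carry-over.* That only restates whichever rates are assumed.

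The conclusion assumes that some ADA present at entry is still detectable at Week 76 or later. If none is, the count and the true incidence agree, but the plan gives no way to show that.

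**What to change.** In the IM Set definition and SAP 2.5:
- State that the core Week 60 ADA result is the Week 60E1 baseline and belongs to the IM Set despite the extension-only wording. If it is missing, use the last core result and flag it. State how participants with no core result are handled.
- Report as incidence the treatment-emergent ADA: negative at baseline and positive later, with baseline-negative participants as the denominator, by extension arm.
- Report ADA present at baseline separately in a shift table by extension arm, preferably also by core dose.
- Say whether the first dose of iscalimab that defines the ADA visits is the core or the extension dose.
- Correct the IM Set paragraph, which defines that set but then bases the immunogenicity analysis on the PK Set.

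The cost is SAP wording, one extra table and a slightly smaller denominator. No new sampling is needed if ADA was measured at core Week 60 or earlier in the core study, which these documents do not confirm. If it was not, the table should be labelled as prevalence at each visit.
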